Appendix 9. Criteria for Parkinson’s Disease with Mild Cognitive Impairment

Criteria for the Diagnosis of PD-MCI	
I. Inclusion criteria	
 • Diagnosis of Parkinson’s disease as based on the UK PD Brain Bank Criteria²⁰ • Gradual decline, in the context of established PD, in cognitive ability reported by either the patient or informant, or observed by the clinician • Cognitive deficits on either formal neuropsychological testing or a scale of global cognitive abilities (detailed in section III) • Cognitive deficits are not sufficient to interfere significantly with functional independence, although subtle difficulties on complex functional tasks may be present
II. Exclusion criteria	
 • Diagnosis of PD dementia based on MDS Task Force proposed criteria¹⁸ • Other primary explanations for cognitive impairment (e.g., delirium, stroke, major depression, metabolic abnormalities, adverse effects of medication, or head trauma) • Other PD-associated comorbid conditions (e.g., motor impairment or severe anxiety, depression, excessive daytime sleepiness, or psychosis) that, in the opinion of the clinician, significantly influence cognitive testing
III. Specific guidelines for PD-MCI level I and level II categories	
A. Level I (abbreviated assessment)
 
 • Impairment on a scale of global cognitive abilities validated for use in PD^a or • Impairment on at least two tests, when a limited battery of neuropsychological tests is performed (i.e., the battery includes less than two tests within each of the five cognitive domains, or less than five cognitive domains are assessed) 
B. Level II (comprehensive assessment)
 
 • Neuropsychological testing that includes two tests within each of the five cognitive domains (i.e., attention and working memory, executive, language, memory, and visuospatial)^b • Impairment on at least two neuropsychological tests, represented by either two impaired tests in one cognitive domain or one impaired test in two different cognitive domains • Impairment on neuropsychological tests may be demonstrated by: 
 – Performance approximately 1 to 2 SDs below appropriate norms or – Significant decline demonstrated on serial cognitive testing or – Significant decline from estimated premorbid levels
IV. Subtype classification for PD-MCI (optional, requires two tests for each of the five cognitive domains assessed and is strongly suggested for research purposes)^c	
 • PD-MCI single-domain—abnormalities on two tests within a single cognitive domain (specify the domain), with other domains unimpaired or • PD-MCI multiple-domain—abnormalities on at least one test in two or more cognitive domains (specify the domains)

^aSee Table 2. Examples of scales of global cognitive abilities validated in PD.

^bSee Table 3. Examples of neuropsychological tests for the five cognitive domains.

^cSubtype classifications are applicable only to those PD-MCI who have had at least two tests within each of the five cognitive domains administered.

Reprinted with permission from Litvan 2012.

Appendix 10. Parkinson’s Disease with Dementia Criteria

Features of dementia associated with Parkinson’s disease	

I. Core features
 
 1. Diagnosis of Parkinson’s disease according to Queen Square Brain Bank criteria 2. A dementia syndrome with insidious onset and slow progression, developing within the context of established Parkinson’s disease and diagnosed by history, clinical, and mental examination, defined as: 
 • Impairment in more than one cognitive domain • Representing a decline from premorbid level • Deficits severe enough to impair daily life (social, occupational, or personal care), independent of the impairment ascribable to motor or autonomic symptoms 
II. Associated clinical features
 
 1. Cognitive features: 
 • Attention: Impaired. Impairment in spontaneous and focused attention, poor performance in attentional tasks; performance may fluctuate during the day and from day to day • Executive functions: Impaired. Impairment in tasks requiring initiation, planning, concept formation, rule finding, set shifting or set maintenance; impaired mental speed (bradyphrenia) • Visuo-spatial functions: Impaired. Impairment in tasks requiring visual-spatial orientation, perception, or construction • Memory: Impaired. Impairment in free recall of recent events or in tasks requiring learning new material, memory usually improves with cueing, recognition is usually better than free recall • Language: Core functions largely preserved. Word finding difficulties and impaired comprehension of complex sentences may be present 2. Behavioral features: 
 • Apathy: decreased spontaneity; loss of motivation, interest, and effortful behavior • Changes in personality and mood including depressive features and anxiety • Hallucinations: mostly visual, usually complex, formed visions of people, animals or objects • Delusions: usually paranoid, such as infidelity, or phantom boarder (unwelcome guests living in the home) delusions • Excessive daytime sleepiness 
III. Features which do not exclude PD-D, but make the diagnosis uncertain
 
 • Co-existence of any other abnormality which may by itself cause cognitive impairment, but judged not to be the cause of dementia, e.g. presence of relevant vascular disease in imaging • Time interval between the development of motor and cognitive symptoms not known 
IV. Features suggesting other conditions or diseases as cause of mental impairment, which, when present make it impossible to reliably diagnose PD-D
 
 • Cognitive and behavioral symptoms appearing solely in the context of other conditions such as: 
 Acute confusion due to 
 a. Systemic diseases or abnormalities b. Drug intoxication Major Depression according to DSM IV • Features compatible with “Probable Vascular dementia” criteria according to NINDS-AIREN (dementia in the context of cerebrovascular disease as indicated by focal signs in neurological exam such as hemiparesis, sensory deficits, and evidence of relevant cerebrovascular disease by brain imaging AND a relationship between the two as indicated by the presence of one or more of the following: onset of dementia within 3 months after a recognized stroke, abrupt deterioration in cognitive functions, and fluctuating, stepwise progression of cognitive deficits) 	
Criteria for the diagnosis of probable and possible PD-D	

Probable PD-D
 
 A. Core features: Both must be present B. Associated clinical features: 
 • Typical profile of cognitive deficits including impairment in at least two of the four core cognitive domains (impaired attention which may fluctuate, impaired executive functions, impairment in visuo-spatial functions, and impaired free recall memory which usually improves with cueing) • The presence of at least one behavioral symptom (apathy, depressed or anxious mood, hallucinations, delusions, excessive daytime sleepiness) supports the diagnosis of Probable PD-D, lack of behavioral symptoms, however, does not exclude the diagnosis C. None of the group III features present D. None of the group IV features present 
Possible PD-D
 
 A. Core features: Both must be present B. Associated clinical features: 
 • Atypical profile of cognitive impairment in one or more domains, such as prominent or receptive-type (fluent) aphasia, or pure storage-failure type amnesia (memory does not improve with cueing or in recognition tasks) with preserved attention • Behavioral symptoms may or may not be present 
OR
 
 C. One or more of the group III features present D. None of the group IV features present 	

Reprinted with permission from Emre 2007.

Appendix 11. Infusion Administration Manual

1. PURPOSE

The purpose of this Infusion Administration Manual is to guide site staff in administering study drug (GRF6021 or placebo) and maintaining blinding of staff and study subjects. As applicable, sites should follow their own standard operating procedures (SOPs) and processes for intravenous (IV) infusions and the insertion, management, and removal of IV catheters that will be used for the administration of study drug while at the same time adhering to study-specific requirements pertaining to the administration of the study drug.

2. STUDY DRUG

The active study drug is GRF6021, a purified [REDACTED] fraction prepared from large pools of human sourced plasma meeting all specifications [REDACTED]. Each 100 mL of GRF6021 contains [REDACTED] of selected plasma proteins [REDACTED]. The plasma proteins consist of approximately [REDACTED]. The solution is iso-oncotic and isotonic with normal human plasma. The approximate concentrations of significant electrolytes are: [REDACTED]. GRF6021 is clear and [REDACTED] and must be administered intravenously. [REDACTED]

The placebo control agent will be 0.9% sodium chloride injection (saline).

Both active and placebo (hereafter referred to as the “study drug”) are supplied in [REDACTED] glass vials, and a volume of [REDACTED] will be administered on each infusion day.

3. GENERAL INFORMATION

- GRF6021 is contraindicated in subjects with anemia, increased blood volume, or congestive heart failure, and in subjects on cardiopulmonary bypass. Note: ejection fraction as measured with echocardiography should be performed at screening to determine eligibility before dosing occurs.
- During the dosing periods, Pre-infusion Safety Labs will be drawn locally before the infusion starts. These labs must be reviewed before dosing the follow day. The following blood labs must be documented as within normal limits: sodium, potassium, ionized calcium, blood urea nitrogen, creatinine, hematocrit, hemoglobin, and platelets. Pregnancy testing will be required prior to dosing on Visits 3 and 11 in women of childbearing potential (WOCBP).
- The use of a volumetric infusion pump is the preferred method of administration of study drug. The study drug may be infused by gravity with a rate controlling device if a pump is not available or is not operational. The PI or designee must approve this infusion methodology for each individual subject. If a rate-controlling device is used, it must be continuously monitored by the unblinded Infusion Nurse.
- Study drug administration should be performed in a controlled clinical setting such as a physician’s office, Phase 1 unit, or Ambulatory Infusion Center (AIC).

- An appropriately qualified blinded Outcomes Assessor will monitor the subject throughout the infusion and for approximately 4 hours after the infusion has been completed. This person’s qualifications must enable them to identify AEs, monitor vital signs, and take the appropriate course of action when an AE or clinically-significant vital sign change occurs.
- Sites must identify and follow procedures that ensure adequate blinding of blinded study personnel, subjects, and trial partners before, during, and after the Infusion Period. This may include the use of study drug container covers and/or the use of drapes to separate the unblinded Infusion Nurse and infusion apparatus from the blinded Outcomes Assessor, PI, subject, and trial partner.
- The unblinded pharmacist, or other qualified site personnel responsible for drug accountability, must retain all used vials/containers for drug accountability, unless otherwise agreed to with the Sponsor. These should be kept in a secure location with limited access to minimize the risk of unblinding blinded study staff. Partially-used vials/containers may not be re-used.

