GRF6021 is contraindicated in patients with severe anemia, congestive heart failure, or increased blood volume (PI) and these are exclusion criteria in this study. GRF6021 is depleted of the majority of immunogenic proteins during the manufacturing process, and thus is not expected to alter the blood typing characteristics of the recipient and should not sensitize humans to its subsequent administration [REDACTED]. ABO antigen typing is not required prior to administration. GRF6021 is not expected to significantly alter the urinalyses of recipients, their bleeding times, coagulation times, prothrombin times, prothrombin consumption, platelet counts, or fibrinogen levels when given in quantities of up to 1000 mL [REDACTED].

Based on the cumulative review [REDACTED] (PSUR), the production steps taken to increase the safety margin and avoid virus transmissions, and the multiple safety minimization steps implemented in this study, the benefit-risk balance for GRF6021 as an investigative product in PD-MCI and PDD is favorable.

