5 STUDY ENROLLMENT AND WITHDRAWAL

5.1 INCLUSION CRITERIA

In order to be eligible for inclusion, all subjects must meet the following criteria:

1. Aged 40-85 years at time of enrollment, inclusive.
2. Diagnosis of clinically established or clinically probable PD according to MDS-PD criteria (Postuma 2015)(Appendix 8) with at least 1 year of PD symptoms.
3. Diagnosis of PD-MCI (Level I, i.e. impairment on a scale of global cognitive abilities validated for

- use in PD) or probable or possible PDD according to MDS criteria (Litvan 2012, Emre 2007)(Appendix 9).
4. Score on the MoCA of 13-25, inclusive (Nasreddine 2005)(Appendix 1).
 5. Hoehn and Yahr Stages 1-4.
 6. If on dopaminergic therapy (e.g., levodopa, dopamine agonists, monoamine oxidase inhibitors, catechol-O-methyl transferase inhibitors, amantadine), must be on stable dosage at least 4 weeks prior to baseline.
 7. If on medications for cognition (e.g., rivastigmine, galantamine, donepezil, memantine), must be on stable dosage for at least 8 weeks prior to baseline.
 8. If on antidepressant medications, must be on stable dosage for at least 8 weeks prior to baseline.
 9. If on clozapine, quetiapine, or pimavanserin, must be on stable dosage for 8 weeks prior to baseline.
 10. Renal function as defined by estimated glomerular filtration rate (eGFR) ≥ 45 mL/min/1.73 m² using the Modification of Diet in Renal Disease (MDRD) study equation and no microalbuminuria.
 11. Systolic ejection fraction of $\geq 55\%$ on trans-thoracic echocardiogram.
 12. Modified Hachinski Ischemic Scale (MHIS) score of 4 or less (Rosen 1980).
 13. Female subjects must not be pregnant or breastfeeding. Women of childbearing potential (WOCBP) must have a negative pregnancy test at screening (Visit 1), Visit 3 (prior to study treatment), and Visit 11 (prior to study treatment). WOCBP must agree to use highly effective contraception prior to study entry (Clinical Trial Facilitation Group 2014). A woman is considered of childbearing potential following menarche and until becoming postmenopausal (no menses for at least 2 years without an alternative cause). Should a woman become pregnant or suspect she is pregnant while she or her partner is participating in the study, she should inform her treating physician immediately.

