 16. Current, active liver disease or known hepatic or biliary abnormalities.
 17. Uncontrolled diabetes defined as hemoglobin A1c (HbA1c) > 7.5%.
 18. Clinically significant abnormalities in complete blood count, complete metabolic panel, serum albumin, serum lipids, coagulation, or levels of thiamine, pyridoxine, cobalamin, and thyroid stimulating hormone.
 19. Positive urine drug screen. The presence of opioids, benzodiazepines, and/or amphetamines in the urine drug screen may be allowed if these are prescribed and the dose stable for at least 8 weeks prior to screening.
 20. Hemoglobin < 10 g/dL in women and < 11 g/dL in men.
 21. Urine protein-to-creatinine ratio (UPCR) of > 1.5 grams of protein per gram of creatinine.
 22. Inadequate venous access to allow IV drug delivery or multiple blood draws.
 23. Concurrent participation in any other therapeutic treatment trial. If there was prior clinical trial participation, subject must have discontinued investigational agents for at least 30 days for small molecules, and 1 year for active or passive immunotherapies prior to screening.
 24. If on deep brain stimulation (DBS), DBS surgery within 12 months of screening and/or a change in DBS settings within 12 weeks of screening. DBS settings must not be changed at any point during the subject's participation in the trial.
 25. Presence of a pacemaker or any other implant that would be an MRI contraindication, including DBS if not MRI compatible.
 26. More than 2 lacunar strokes or other clinically-relevant imaging abnormality on screening MRI.
 27. Any other condition and/or situation that the investigator believes may interfere with the safety of the subject, study conduct, or interpretation of study data.

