7.2 LABORATORY PROCEDURES/EVALUATIONS

7.2.1 CLINICAL LABORATORY EVALUATIONS

Biological samples (e.g. whole blood, serum, urine) will be collected for laboratory evaluations in accordance with Section 7.1.1.1.11 Screening Safety Lab Panel, Section 7.1.1.2.8 Blood and Urine Collection for Lab Evaluations, and the Schedule of Events. . Clinical sample processing and laboratory evaluations will be conducted by a central lab's registered and certified Clinical Laboratory Improvement Amendments (CLIA) facilities. Pre-infusion laboratory evaluations will be conducted at the clinical site. Refer to the study's laboratory manual for complete information regarding all laboratory evaluations to be performed, sample collection procedures, and related requirements.

The investigator is responsible for determining and documenting whether out of range laboratory values are clinically significant. All clinically significant values will be recorded as AEs in the CRF and followed until determined to be stable or resolved, unless the subject is lost to follow up. Once resolved, the appropriate CRF page(s) will be updated.

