5.2. Prior to Infusion

The blinded Outcomes Assessor will check the following information prior to infusion start:

- a. Subject identification to ensure it is the correct subject.
- b. Verify eligibility criteria (e.g. subject’s history and diagnosis, including allergies and previous reactions to blood or blood products).
- c. Review AEs and concomitant medications.
- d. Baseline vital signs (temperature, seated BP, orthostatic BP, heart rate, respiratory rate, and weight) within 1 hour of the start of the infusion and record data on source document.

- e. Ensure Pre-Infusion Safety Lab and Comprehensive Lab samples are obtained when applicable per the [Schedule of Events](#). The results of the Pre-Infusion Safety Labs should be available and interpreted prior to the following day’s infusion.
- f. The PI or physician designee should perform a targeted physical exam when applicable per the [Schedule of Events](#).
- g. Review and interpret Pre-Infusion Safety Lab results. Refer to **Table 2. Signs or Symptoms Associated with Abnormal Lab Values**.
- h. Confirm with PI that the subject is cleared to begin the infusion.

Table 2. Signs or Symptoms Associated with Abnormal Lab Values

Lab abnormality	Signs and Symptoms	Additional Testing*
Hyponatremia	Lethargy, confusion, nausea, vomiting, muscle cramps or weakness	n/a
Hypokalemia	Weakness, fatigue, muscle cramps or heart palpitations	ECG: Increased amplitude and width of P wave, longer PR interval, T wave flattening, ST depression, prominent U waves
Hypocalcemia	paresthesia, circumoral numbness, laryngospasm, muscle spasms or muscle cramps	ECG: Narrowing QRS, shortening PR interval, T wave flattening, QT prolongation, prominent U-wave, ST depression
Hypoglycemia	Palpitations, dyspnea, confusion, fatigue, shakiness, sweating, irritability, tingling around the mouth, blurred vision, dizziness, sleepiness	n/a
Kidney failure (serum creatinine)	Decreased urine output, edema, drowsiness, fatigue, confusion, nausea, dyspnea	Urinalysis: proteinuria or albuminuria
Anemia (Hct or Hgb)	Dizziness, weakness, headache, cold extremities, numbness, low body temperature, pallor	n/a

*Additional testing may be performed as needed in the event that recent results aren’t available for review.

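### The Infusion Manual requires eight pre-infusion labs to be within normal limits, while the rest of the protocol sends abnormal results to investigator judgement and eligibility does not require normal values

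*Protocol*

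**What the plan says.** **The strict sentence.** Appendix 11 section 3 first asks for the pre-infusion labs to be reviewed before the next day's dosing. It continues: "The following blood labs must be documented as within normal limits", and lists "sodium, potassium, ionized calcium, blood urea nitrogen, creatinine, hematocrit, hemoglobin, and platelets".

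**The other pre-infusion instructions.**
- Protocol section 7.1.1.2.8.2 and note g of the Schedule of Events ask that results be available and interpreted before the infusion they precede. Neither mentions normal limits.
- Appendix 11 section 5.2, step g, says "Review and interpret Pre-Infusion Safety Lab results" and points to a table of signs and symptoms for abnormal values, with rows for creatinine and for hematocrit or hemoglobin. Step h then asks for the investigator's clearance.
- Appendix 11 section 5.4 c requires the source record to show the investigator's review, any abnormal values, and the interpretation or decision.

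**Eligibility.**
- Exclusion 20 is "Hemoglobin < 10 g/dL in women and < 11 g/dL in men".
- Inclusion 10 requires an MDRD eGFR of at least 45 mL/min/1.73 m² and no microalbuminuria. It sets no creatinine or BUN limit.
- Exclusion 18 covers "Clinically significant abnormalities in complete blood count, complete metabolic panel, serum albumin, serum lipids, coagulation" and some further tests, so it acts only on abnormalities judged clinically significant.
- Protocol section 7.2.1 keeps that judgement separate from being out of range: "The investigator is responsible for determining and documenting whether out of range laboratory values are clinically significant".

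**The contraindication.** Protocol section 2.3.1 says "GRF6021 is contraindicated in patients with severe anemia, congestive heart failure, or increased blood volume" and adds that these are exclusion criteria. Appendix 11 section 3 lists anemia with no qualifier.

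**The concern.** The strict sentence uses mandatory wording and sits next to the dosing requirement, so a site can fairly read it as a condition for giving the next infusion. The other instructions assume that an abnormal result can reach the investigator and be decided on. A subject can meet every eligibility criterion and still have a hemoglobin, hematocrit, creatinine or BUN outside the local range.

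The protocol allows up to 40 sites, each using its own laboratory or a handheld analyzer. The same result could be dosed through at one site and held at another. Because the manual is part of the protocol, either action can be called a departure from some passage, and section 13.3 defines a deviation as any noncompliance. The SAP (section 9.2) says the pre-infusion results stay at the sites and will not be summarized, so the planned tables would not link a missed infusion to the value behind it. What is at stake is the number of doses received and membership of the efficacy analysis sets.

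**Working it through.** The plan states no figure on this point. The check compares the passages and counts infusions.

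**1. Analytes.** The list in Appendix 11 section 3 has 8 entries, the same 8 as Protocol section 7.1.1.2.8.2.

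**2. Infusions preceded by a scheduled pre-infusion lab** (section 7.1.1.2.8.2; infusion numbers from the Schedule of Events).

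| Local-laboratory draw | Handheld draw, same day | Infusion that follows |
|---|---|---|
| Visit 3 | Visit 4 | 2 |
| Visit 4 | Visit 5 | 3 |
| Visit 6 | Visit 7 | 5 |
| Visit 11 | Visit 12 | 7 |
| Visit 12 | Visit 13 | 8 |
| Visit 14 | Visit 15 | 10 |

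Six of the 10 infusions follow a scheduled lab. Infusions 1, 4, 6 and 9 follow no new one.

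**3. One held infusion.** Section 7.3.4 and note b of the Schedule of Events give a 6-day window for 5 infusions, so 6 − 5 = 1 spare day per course. An infusion held once may be given on that day. The documents do not say whether an out-of-range lab qualifies for the grace day, or whether the test is repeated. If the infusion is not recovered, 10 − 1 = 9 doses. The SAP's Per Protocol Set needs all 10, and the Complete Set is nested within it, so the subject leaves both.

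**4. A persistently out-of-range value.** If all six lab-preceded infusions are withheld, 10 − 6 = 4 remain (1, 4, 6 and 9). The Evaluable Set needs at least 5, along with its other conditions. This is a maximum: a site that carried an out-of-range result forward to infusions 4 or 9 would give fewer. If infusions 4 and 9 go ahead, withholding five of the six still leaves 10 − 5 = 5, which meets the dose requirement. Loss from the Evaluable Set by this route therefore needs repeated withholding across both courses.

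**5. Safety Set.** Infusion 1 follows no scheduled pre-infusion lab. The Safety Set needs any amount of study agent (Protocol section 10.3) or at least one dose (SAP section 5). Membership does not depend on the later infusions.

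**6. Eligibility against normal limits.** The hemoglobin gap exists wherever the local lower limit is above 10 g/dL for women or 11 g/dL for men. Section 2.3.1 treats severe anemia as the exclusion, which implies that lesser anemia can be enrolled. That supports the gap but does not prove it. eGFR is not one of the eight labs; the renal link runs through creatinine and BUN, for which eligibility sets no limit.

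**The case against.** The best reply is that the manual should be read as a whole. The strict sentence states no hold or stop. Steps g and h of section 5.2, the table for abnormal values and section 5.4 c all assume that abnormal results occur and that the investigator decides. On that reading the defect is one loosely worded summary sentence. Eligibility is also tighter than exclusion 20 and the eGFR limit suggest: exclusion 15 removes hypocalcemia of any kind, exclusion 18 removes clinically significant abnormalities, and inclusion 10 rules out microalbuminuria.

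Much of this stands, and it narrows the gap. It does not remove the conflict. The sentence is mandatory, carries no exception, and comes before the operational steps. No passage defines normal limits or says what happens to the infusion when a value lies outside them.

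Some stronger readings are tempting, but the documents do not support them:
- *Infusions 2–5 and 7–10 are all blocked.* Infusions 4 and 9 follow no new scheduled lab.
- *Any held infusion costs Per Protocol membership.* The grace day may recover it.
- *Isolated missed doses remove subjects from the Evaluable Set.* That set needs only 5 of 10 doses.
- *The primary analysis is compromised.* It uses the Safety Set.
- *A failure rate can be attached.* If each normal range were a central 95% interval, the chance of at least one of 8 values falling outside at one draw would run from 5% (fully dependent) to 1 − 0.95⁸ = 33.7% (independent). The documents give no ranges. Hemoglobin and hematocrit are related, as are BUN and creatinine, and repeat draws come from the same subject. No rate is relied on here.

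**Conclusion.** The contradiction is in the current text and should be fixed. The manual's section 3 requires eight normal results. The rest of the protocol and manual sends abnormal results to investigator judgement, eligibility does not require normal values, and the contraindication is worded two ways.

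Taken literally, the rule reaches 6 of 10 infusions. An unrecovered hold costs membership of the Per Protocol and Complete Sets. A value that stays out of range could cap a subject at 4 infusions, below the Evaluable threshold. The Safety Set and the primary analysis population are not affected, and the efficacy endpoints at risk are declared unpowered.

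These counts assume that the strict sentence is applied only to the infusion that follows a scheduled draw. Whether an eligible subject is caught depends on local laboratory ranges, so the number affected cannot be given.

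**What to change.** The sponsor's medical team should reconcile these places:
- Appendix 11 section 3 (the normal-limits sentence and the anemia contraindication), section 5.2 (steps g and h) and section 5.4 c;
- Protocol section 7.1.1.2.8.2 and Schedule of Events note g;
- inclusion 10, and exclusions 18 and 20;
- the contraindication in section 2.3.1.

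One consistent rule should appear in all of them, including what happens to the infusion when a value is out of range. Which rule is clinically right is for that team, and none is proposed here.

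The cost is protocol and manual wording plus a site clarification memo. Sample size, endpoints and analysis methods do not change.
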